5.3 Pre-treatment/Concomitant Medications/Procedures

Number and proportion of patients taking pre-treatment/concomitant medications and rescue medications will be summarized, sorted by decreasing frequency of ATC Level 2 (therapeutic main group) and ATC level 4 (chemical/therapeutic subgroup), based on the overall incidence across treatment groups.

Procedures will be summarized by treatment group by primary SOC (sorted by internationally agreed order) and PT (sorted in alphabetical order), sorting are based on the overall incidence across treatment groups.

The detailed information of rescue medications/procedures including duration of use and incidence of use will be summarized by topical and systemic groups. Kaplan Meier curves for time to first rescue use will be generated. Listing of rescue use will be presented.

The compliance of moisturizers (emollients) used from 7 days before the baseline visit to end of study, which is defined as the (number of days moisturizers used during the period) / (number of days within the period) x 100%, will be summarized by treatment group.

5.4 Patient Disposition

The following summaries by table will be provided:

- The total number of screened patients: patients who signed the informed consent
- The total number of randomized patients: patients with a treatment kit number allocated and recorded in the IRT database, and regardless of whether the treatment kit was used or not
- The total number of patients in each analysis population

- The total number of patients who discontinued the study treatment and the reasons for the discontinuation
- The total number of patients who discontinued the study, and the reasons for discontinuation

The following listings will be provided:

- Listing of patient disposition including: date of randomization, last visit, dosing, completed study drug or discontinued by reason, completed study or discontinued by reason
- A listing of patients treated but not randomized, patients randomized but not treated, and patients randomized but not treated as randomized
- Summary table with listing of protocol deviations will be provided

5.5 Dose administration

A given administration will be considered noncompliant if the patient did not take the planned dose of treatment as required by the protocol. The compliance with protocol-defined study treatment will be calculated as follows:

Treatment compliance= (number of IMP injections during exposure period)/(number of planned IMP injections during exposure period) x 100%

Loading doses for the same patient will be counted as 1.

Summary of study drug administration will include the number of study drug doses administered and treatment compliance. The treatment compliance will be summarized descriptively and will be presented by the following specific ranges for each treatment group: <80%, 80% - 120%, and >120%.

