2 INVESTIGATIONAL PLAN

2.1 Study Design and Randomization

This is a randomized, double-blind, placebo-controlled, parallel-group phase 3 study to evaluate the efficacy and safety of dupilumab monotherapy in adults with moderate-to-severe AD. The study period included 16-week treatment period 12-week follow-up. Eligible patients will be randomized in a 1:1 ratio to receive q2w SC injections of 300 mg dupilumab, or matching placebo. Randomization will be stratified by baseline disease severity (moderate [Investigator's Global Assessment (IGA) 3] versus severe [IGA 4] AD).

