2.3 Study Plan

The study consists of a screening period, a treatment period and a follow-up period as presented below:

¹ Patients will receive a loading dose of the IMP on Day 1 and then receive the IMP every two weeks during the subsequent 14 weeks.

IMP = investigational medicinal product, q2w = once every 2 weeks.

After providing informed consent, patients will be assessed for study eligibility at the screening visit. Patients will undergo screening for 7-35 days prior to randomization. During the screening period, treatments for AD will be washed out, as applicable, according to eligibility requirements.

Patients may be rescreened once if they fail the screening evaluation for reasons related to incidental transitory conditions. Patients will be required to apply moisturizers (emollients) at least twice daily for at least 7 days before randomization and continue throughout the study. However, to allow adequate assessment of skin dryness, moisturizers should not be applied on the area(s) of nonlesional skin designated for such assessments for at least 8 hours before each clinic visit.

Patients who continue to meet eligibility criteria at baseline will undergo Day 1/baseline assessments and will be randomized to receive q2w SC injections of 300 mg dupilumab following a loading dose of 600 mg on Day 1, or matching placebo (including doubling the amount of placebo on Day 1 to match the loading dose). Eligible patients must have a documented history of inadequate response or intolerance to treatment with topical AD medications. Following the initial dose of 600 mg, the investigational medicinal product (IMP) will be administered 300 mg at Weeks 2, 4, 6, 8, 10, 12, and 14. Patients will remain at the study site for a minimum of 30 minutes after each injection at the study site. Patients will have the option to self-administer the IMP (or have a caregiver administer the IMP) outside the study site during weeks in which no clinic visit is scheduled (ie, Weeks 6, 10, and 14). Patients (and/or caregivers) will be trained on injecting the IMP at Visit 2 (Day 1) through Visit 4 (Week 4), or until competency has been demonstrated. Patients who do not want to self-inject may have the clinic staff administer all the IMP injections in the clinic.

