3.2 Per Protocol Population

The per protocol (PP) population includes all patients in the ITT population except for those who are excluded because of major efficacy-related protocol violations.

A major efficacy-related protocol violation is one that may affect the interpretation of study efficacy results. The criteria of major efficacy-related protocol deviation are defined as following:

- Patients who did not receive treatment as randomized, which are defined as
 - patients on placebo but accidentally exposed to dupilumab,
 - patients on dupilumab receiving placebo whose compliance with the dupilumab injection is <80% by counting placebo injections as missing
- Any major violations of efficacy-related entry criteria ([Appendix 10.7](#))
 - Inclusion criteria 3, 4, 5 and 6
 - Exclusion criteria 3, 4, 5, 6, 7, 8 and 9
- The percentage of a patient's compliance with the IMP injection is <80% or >120% of the scheduled doses during the study treatment period
- Patients who were randomized more than once
- Patients who were randomized but not treated

Final determination of the PP population will be made in the blinded manner prior to the database lock.

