3.3 Safety Population

The safety population consists all randomized patients who receive any IMP. Patients will be analyzed according to the treatment they actually received (as treated).

The actual treatment group is defined by the following rules:

- For patients on placebo but accidentally exposed to dupilumab, the treatment group allocation for as-treated analysis will be dupilumab
- For patients on dupilumab but accidentally received placebo, the actual treatment group allocation for as-treated analysis will be the treatment as randomized if at least one dose or part of a dose of dupilumab was received
- For patients on dupilumab but accidentally received placebo, the actual treatment group allocation for as-treated analysis will be placebo if the patient did not exposed to any dupilumab

In addition:

- Nonrandomized but treated patients will not be part of the safety population, but their safety data will be presented separately
- Randomized patients for whom it is unclear whether they took the IMP will be included in the safety population as randomized

Treatment compliance/administration and all clinical safety variables will be analyzed using the safety population.

The pre-treatment period is defined as the time from signing the informed consent form (ICF) to before the first dose of IMP. The treatment emergent period is defined as the time from first dose of IMP (Day 1) to the end of the study.

For safety summarizes, three analysis period are defined as follows:

- On-treatment period is defined as day 1 to the day of last dose of IMP + 14 days or early termination date from study, whichever comes first
- Follow-up period is defined as the last dose of IMP + 15 days to the date of the end of study
- Overall study period is defined as day 1 to the date of the end of study, consisting of both the treatment and follow-up periods

The safety population will be the basis for the analyses for the week 16 treatment period and overall study period; however, for the analyses for the follow-up period, only a subset of safety population will be included, which is defined as the patients who entered the follow-up and had at least one visit after week 16 treatment visit.

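### Does the undefined exposure period in the compliance formula leave per-protocol membership unclear for patients who stop early?

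*SAP*

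**What the plan says.** SAP 5.5 holds the SAP's only formula for compliance with study drug: "Treatment compliance= (number of IMP injections during exposure period)/(number of planned IMP injections during exposure period) x 100" per cent, with the loading injections counted as one. Protocol 11.4.2.2 has the same ratio. The SAP introduces it with "The compliance with protocol-defined study treatment will be calculated as follows" and tabulates the result in three bands cut at 80% and 120%. Neither document says when the exposure period ends.

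The PP population is defined in SAP 3.2 and Protocol 11.3.1. Both exclude a patient whose "compliance with the IMP injection is <80% or >120% of the scheduled doses during the study treatment period". SAP 3.2 adds a criterion for patients randomised to dupilumab who were given placebo in error; it removes those "whose compliance with the dupilumab injection is <80% by counting placebo injections as missing" and names no denominator. The section closes with "Final determination of the PP population will be made in the blinded manner prior to the database lock".

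The schedule is fixed. SAP 2.1 states "The study period included 16-week treatment period 12-week follow-up", and SAP 2.3 says that after the Day 1 loading dose the drug "will be administered 300 mg at Weeks 2, 4, 6, 8, 10, 12, and 14".

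Two nearby definitions follow the patient's own last dose. SAP 5.6 computes duration of exposure as last minus first injection date plus 14 days. SAP 3.3, for safety summaries, has "On-treatment period is defined as day 1 to the day of last dose of IMP + 14 days", or early termination if that is sooner.

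**The concern.** The formula and the PP rule share their limits but not their denominators. A programmer who has already derived a compliance variable for the SAP 5.5 table might reuse it for PP. If the exposure period is then tied to the patient's last dose, doses planned after stopping drop out of the denominator, and a patient who took half the course can look fully compliant.

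This would matter for the PP analysis of the primary endpoint because no other PP criterion removes a treated patient for stopping early. Such patients are asked to attend the remaining visits. SAP 5.7.1 sets rescue, withdrawal and missing data to non-response, but not stopping study drug as such. A patient last dosed at Week 6 could therefore enter the PP analysis with a Week 16 IGA taken 10 weeks after the last dose.

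**Working it through.** The plan gives no compliance result to reproduce, only the limits of 80% and 120%.

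**Inputs.** Dosing occasions are Day 1 plus Weeks 2 to 14, which is 1 + 7 = 8 (SAP 2.3), on days 1, 15, 29, 43, 57, 71, 85 and 99. The loading dose counts as one (SAP 5.5). The dosing window is ±3 days (Protocol 8.1.3). Assumptions: the first dose is given, there are no extra injections, planned days stay fixed, and the patient remains in the study.

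**PP wording.** Compliance is doses received / 8. The limit is 0.80 × 8 = 6.4, so at least 7 occasions are needed. Counting the loading dose as two injections leaves the cut in the same place: 7/9 = 77.8% for six occasions and 8/9 = 88.9% for seven.

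**Formula, fixed reading.** If the exposure period is the 16-week treatment period, the denominator is again 8 and the two agree for every dosing pattern.

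**Formula, patient-specific readings.** The table takes a patient who receives k consecutive doses on time and then stops. A window of last minus first plus 14 days, counted from Day 1, ends 13 days after the last dose. The SAP 3.3 period ends on day 14, which is the next planned dosing day, so one more planned dose enters its denominator.

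| k | PP wording, k/8 | Period ends at last dose or 13 days later | Period ends 14 days after last dose, inclusive |
|---|---|---|---|
| 1 | 12.5% | 100% | 1/2 = 50% |
| 2 | 25% | 100% | 2/3 = 66.7% |
| 3 | 37.5% | 100% | 3/4 = 75% |
| 4 | 50% | 100% | 4/5 = 80% |
| 5 | 62.5% | 100% | 5/6 = 83.3% |
| 6 | 75% | 100% | 6/7 = 85.7% |
| 7 | 87.5% | 100% | 7/8 = 87.5% |
| 8 | 100% | 100% | 100% |

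The formula and the PP wording disagree for k = 1 to 6 in the third column and for k = 4 to 6 in the fourth (80% is not below 80%).

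Dose timing within the window blurs the two patient-specific readings. With the last dose 1 to 3 days late, the 13-day version takes the fourth-column values. With it 1 to 3 days early, the 14-day version takes the third-column values. The exception is k = 1, where Day 1 cannot shift. Stopping after 4, 5 or 6 doses is discordant under both versions at every in-window timing.

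**Intermittent misses.** There are 29 possible pairs of doses received and last occasion dosed. The number in PP by the formula but out by the PP wording is:

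- fixed reading: 0;
- 13-day version: 9 with the last dose on time or early, 4 with it late;
- 14-day version: 8 with the last dose early, 3 with it on time or late.

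No pair moves the other way. The patient-specific denominator never exceeds 8, so the formula can only raise the ratio. These are dosing patterns, not patients.

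**Mis-dispensing criterion.** Anyone with 6 or fewer occasions is already out under the general rule, and a patient dosed at Week 14 has a denominator of 8 either way. The choice matters only for someone who takes all seven doses to Week 12, exactly one of them placebo, and then stops: 6/8 = 75% against 6/7 = 85.7%.

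**Which text governs PP.** SAP 3.2 names the doses that count and the period they belong to, and SAP 2.1 and 2.3 supply both. It does not refer to 5.5, and 5.5 does not claim to decide PP membership. The PP derivation needs nothing from the formula except the convention that the loading dose is one.

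**The case for a change.** The strongest case for acting is practical. There is one compliance formula, it is reported in the PP rule's own bands, and the next section of the SAP measures exposure to the patient's last injection. A patient-specific reading is therefore natural, and reusing the variable for PP would be an easy mistake. Blinded determination prevents a choice driven by treatment but does not supply the missing definition, and the SAP exists to pre-specify such things.

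Part of this stands. The term is undefined, and the compliance table could be produced on either basis. The SAP's reference to protocol-defined treatment, which Protocol 11.4.2.2 lacks, leans towards the full schedule, but it does not settle the matter.

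The step from there to PP does not stand. A programmer would have to set aside a rule that states its own denominator, import a ratio from a section that SAP 3.2 does not cite, and then choose a patient-specific reading of it. Shared cut-points suggest a link but do not make one. Share of the full course received and adherence while on treatment are different quantities, and a plan can carry both. The mis-dispensing criterion sits in the same list as the scheduled-dose rule, so the same denominator is its natural reading.

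**Conclusion.** No change is needed. This is a gap in a descriptive definition that analysts fill sensibly, and the PP rule is complete without it. Followed as written, the plan puts a patient in PP on this criterion with at least 7 of 8 occasions, and early stoppers after 1 to 6 doses are out. Changing SAP 3.2 would only restate that denominator.

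If the formula were wrongly used for PP, patients stopping after 4 to 6 doses would be retained under either patient-specific version. Those stopping after 1 to 3 could also be retained, depending on the version and the dose timing. The documents give no discontinuation rate, so neither the number of such patients nor the direction of any shift in the PP estimate can be computed. The exposure is limited to a supportive analysis whose population is settled blind before lock, and to one descriptive table. The ITT primary analysis, the testing hierarchy and the sample size of 80 per arm do not use compliance. The conclusion rests on reading the PP wording at face value and on the dosing assumptions listed with the calculation.

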5.6 Treatment Exposure and Observation Period

The duration of IMP exposure during the study will be presented by treatment and calculated as:

(Date of last IMP injection – date of first IMP injection) + 14 days regardless of unplanned intermittent discontinuations.

The duration of exposure during the study will be summarized for each treatment group using number of patients, means, SD, minimums, medians, and maximums.

In addition, the duration of exposure will be summarized categorically by counts and percentages for each of the following categories and cumulatively by these categories as well:

≥ 14 days, ≥ 28 days, ≥ 42 days, ≥ 56 days, ≥ 70 days, ≥ 84 days, ≥ 98 days, ≥ 112 days.

The duration of observation period during the study is calculated as:

(Date of the last study visit – date of the first IMP injection) +1.

The duration of observation period will be summarized descriptively as a quantitative data (n, mean, SD, median, minimum and maximum). In addition, the number (%) of patients with observation periods will be presented by specific time periods. The time periods of interest is specified as:

≥ 15 days, ≥ 29 days, ≥ 43 days, ≥ 57 days, ≥ 71 days, ≥ 85 days, ≥ 99 days, ≥ 113 days, ≥ 141 days, ≥ 169 days, ≥ 197 days.

5.7 Analyses of Efficacy Variables

For all efficacy variables, the analysis will be comparisons of dupilumab and the placebo treatment groups. The following null and alternative hypotheses for the primary endpoint will be tested:

H0: No treatment difference between dupilumab and placebo ($p_{dupilumab} = p_{placebo}$, where p stands for the proportion of responders in a treatment group)

H1: There is a treatment difference between dupilumab and placebo ($p_{dupilumab} \neq p_{placebo}$)

The analyses of efficacy variables are described in the subsections below and summarized in [Appendix 10.1](#).

Subgroups are defined by key baseline factors recorded on the CRF and listed to be considered for primary and secondary (EASI and/or Pruritus NRS) efficacy analyses:

- Age group (≥ 18 - <40 , ≥ 40 - <65 , ≥ 65)
- Sex (Male, Female)
- Duration of AD (< 26 years, ≥ 26 years)
- Baseline weight group (< 70 kg, ≥ 70 - <100 kg, ≥ 100 kg)
- BMI (< 15 , ≥ 15 - <25 , ≥ 25 - <30 , ≥ 30)
- Baseline disease severity [moderate (IGA=3) and severe (IGA=4)]
- Baseline moderated-to-severe EASI (< 20 , ≥ 20)
- Baseline severe EASI (< 25 , ≥ 25)
- Baseline peak pruritus NRS (< 7 , ≥ 7)
- Baseline Body Surface Area (BSA) ($\geq 10\%$ - $<30\%$, $\geq 30\%$ - $<50\%$, $\geq 50\%$)
- Previous use of systemic immunosuppressants (Yes, No)
- Previous use of systemic cyclosporine (Yes, No), and/or Azathioprine (Aza) (Yes, No), and/or Methotrexate (MTX) (Yes, No)
- History of asthma (Yes, No)
- History of nasal polys (Yes, No)
- History of allergic rhinitis (Yes, No)
- History of food allergies (Yes, No)

5.7.2 Analyses of Secondary Efficacy Variables

The binary secondary efficacy endpoints will be analyzed using the same approach as that used for the analysis of the primary endpoints.

The continuous endpoints will be analyzed using the multiple imputation (MI) with analysis of covariance (ANCOVA) model as the primary analysis. Patients' efficacy data after rescue medication or procedure up to Week 16 or after study withdrawal up to Week 16 will be set to missing and then imputed by the MI method. Missing data from the ITT population will be imputed 50 times to generate 50 complete data sets by using the SAS MI procedure (using Markov Chain Monte Carlo method) following the 2 steps below:

Step 1: The monotone missing pattern is induced by Markov Chain Monte Carlo (MCMC) method in MI procedure. The monotone missing pattern means that if a patient has missing value for a variable at a visit, then the values at all subsequent visits for the same variable are all missing for the patient.

Step 2: The missing data at subsequent visits will be imputed using the regression method for the monotone pattern with adjustment for covariates including treatment group, randomization strata (disease severity), and relevant baseline value.

The Week 16 data of each of the 50 complete datasets will be analyzed using an ANCOVA model with treatment, randomization strata (disease severity), and relevant baseline value included in the model, and the SAS MIANALYZE procedure will be used to generate valid statistical inferences by combining results from the 50 analyses using Rubin's formula.

The imputation model will include:

- The variables in the ANCOVA model, including treatment group, randomization strata and relevant baseline value
- Measured continuous endpoint values in each scheduled visit up to Week 16

Categorical variables included in above model (ie, treatment group and randomization strata) are not expected to be missing.

To account for the impact of rescue medication or procedure or dropouts on the efficacy effect:

- If a patient receives rescue medication or procedure that specifies the patient as a non-responder according to the above rules for binary efficacy endpoints, the data collected after rescue medication or procedure is initiated will be treated as missing.
- If a patient withdraws from the study, the data collected after study withdrawal will be treated as missing

Sensitivity analyses

In addition to the MI method described previously, sensitivity analyses for the continuous endpoints for EASI and/or Pruritus NRS will be conducted as described below:

1. This sensitivity analysis will use a mixed-effect model repeated measures (MMRM). The model will include factors (fixed effects) for treatment, randomization strata, visit, treatment-by-visit interaction, and relevant baseline values. An unstructured covariance matrix will be used to model the within-patient errors. Denominator degrees of freedom will be estimated using approximation of SATTERTH. The efficacy data will be set to missing after rescue medication or procedure is used or after study withdrawal. Afterwards no imputation will be made.

The MMRM model will provide baseline adjusted least-squares (LS) means at Week 16 and at other time points for each treatment group with the corresponding standard error and the confidence interval, as well as the p values for treatment comparisons. The graph of LS-mean +/- SE by visit will be provided.

2. The sensitivity analysis based on all observed data regardless if rescue treatment is used or if data are collected after withdrawal using MI method will be performed.
3. This sensitivity analysis will use ANCOVA model, including the treatment group, randomization strata and relevant baseline value. The efficacy data will be set to missing after rescue medication or procedure is used or after study withdrawal. The post-baseline LOCF method will then be used to impute missing values.
4. This sensitivity analysis will use ANCOVA model, including the treatment group, randomization strata and relevant baseline value. The efficacy data will be set to missing after rescue medication or procedure is used or after study withdrawal. The post-baseline WOCF method will then be used to impute missing values.

Multiplicity Considerations

If the primary endpoint is significant at the 0.05 level, the secondary endpoints will be tested following the hierarchical testing procedure with a pre-specified order, that is, inferential conclusions about successive secondary endpoints require statistical significance at the 0.05 significance level of the prior one.

The hierarchy for the secondary endpoints is as follows:

- Proportion of patients with EASI-75 response (reduction of EASI score $\geq 75\%$ from baseline) at Week 16

- Proportion of patients with reduction of weekly average of peak daily Pruritus NRS ≥ 4 from baseline to Week 16
- Proportion of patients with reduction of weekly average of peak daily Pruritus NRS ≥ 3 from baseline to Week 16
- Percent change from baseline to Week 16 in weekly average of peak daily Pruritus NRS
- Change from baseline to Week 16 in weekly average of peak daily Pruritus NRS
- Percent change in EASI score from baseline to Week 16
- The proportion of patients with EASI-50 ($\geq 50\%$ improvement from baseline) at Week 16
- The proportion of patients with EASI-90 ($\geq 90\%$ improvement from baseline) at Week 16
- Change from baseline to Week 16 in percent BSA of AD involvement
- Change from baseline to Week 16 in DLQI
- Change from baseline to Week 16 in POEM
- Percent change from baseline to Week 2 in weekly average of peak daily Pruritus NRS

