11.4.3.2 Analyses of secondary efficacy endpoints

For binary endpoints, the secondary efficacy analysis will use the same approach as that used for the primary analysis.

The continuous endpoints will be analyzed using the MI with ANCOVA model as the primary analysis. Patients' efficacy data after rescue medication up to Week 16 will be set to missing and then imputed by the MI method. Missing data will be imputed 50 times to generate 50 complete data sets by using the SAS MI procedure (using Markov Chain Monte Carlo method). The Week 16 data of each of the 50 complete datasets will be analyzed using an ANCOVA model with treatment, randomization strata (disease severity), and relevant baseline value included in the model, and the SAS MIANALYZE procedure will be used to generate valid statistical inferences by combining results from the 50 analyses using Rubin's formula.

The imputation model will include

- The variables in the ANCOVA model, including treatment group, randomization strata and relevant baseline value.
- Measured continuous endpoint values in each scheduled visit up to Week 16

Categorical variables included in above model (ie, treatment group and randomization strata) are not expected to be missing.

To account for the impact of rescue medication or procedure on the efficacy effect:

- Continuous efficacy endpoints: if a patient receives rescue medication or procedure that specifies the patient as a non-responder according to the above rules for binary efficacy endpoints, the data collected after rescue medication or procedure is initiated will be treated as missing.
- If a patient withdraws from the study, this patient will be counted as a non-responder for endpoints after withdrawal.

The mixed-effect model repeated measures (MMRM) will be used to assess the robustness of the analysis with regards to handling of missing data. The MMRM model includes factors (fixed effects) for treatment, randomization strata, visit, treatment-by-visit interaction, and relevant baseline values. It will provide baseline adjusted least-squares means at Week 16 and at other time points for each treatment group with the corresponding standard error and the confidence interval, as well as the p values for treatment comparisons.

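### The MMRM sensitivity analysis holds the baseline and stratum effects constant over visits, so it differs from the Week 16 MI-ANCOVA in covariate adjustment as well as in missing-data handling

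*SAP*

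**What the plan says.** **The MMRM.** SAP 5.7.2 (sensitivity analysis 1) states: "The model will include factors (fixed effects) for treatment, randomization strata, visit, treatment-by-visit interaction, and relevant baseline values". Protocol 11.4.3.2 gives the same list: "The MMRM model includes factors (fixed effects) for treatment, randomization strata, visit, treatment-by-visit interaction, and relevant baseline values". The SAP adds: "An unstructured covariance matrix will be used to model the within-patient errors". Neither document adds a baseline-by-visit or stratum-by-visit term anywhere.

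**Its purpose and scope.** The protocol says the MMRM "will be used to assess the robustness of the analysis with regards to handling of missing data". In the SAP, "sensitivity analyses for the continuous endpoints for EASI and/or Pruritus NRS will be conducted", and the MMRM is to deliver "baseline adjusted least-squares (LS) means at Week 16 and at other time points for each treatment group", together with standard errors, confidence intervals, p-values and a by-visit plot.

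**The analysis it checks.** For the main analysis of continuous endpoints, SAP 5.7.2 says: "The Week 16 data of each of the 50 complete datasets will be analyzed using an ANCOVA model with treatment", randomization stratum and baseline. Imputation comes first: MCMC to reach a monotone pattern, then regressions for the later visits that adjust for the same covariates. Both the main analysis and the MMRM set data to missing after rescue or study withdrawal.

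**The other sensitivity analyses.** Analysis 2 repeats MI on all observed data. Analyses 3 and 4 keep the ANCOVA covariates and replace MI with LOCF and WOCF.

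**The concern.** A sensitivity analysis for missing data is easiest to read when only the missing-data handling changes. Here the covariate adjustment changes too. The ANCOVA uses only Week 16 data to estimate the baseline and stratum effects. The MMRM estimates each as one value shared by Weeks 2, 4, 8, 12 and 16.

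For absolute change, a varying baseline slope is plausible. If nobody has changed, the slope of change on baseline is 0. If everyone has cleared, change equals minus baseline and the slope is -1. EASI has a floor of 0 (SAP 4.4.2), and the sample size section expects 37% versus 12% IGA responders at Week 16. More patients should therefore be near the floor at Week 16 than at Week 2.

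If the slopes do differ, two things follow. The MMRM estimates carry avoidable noise, and a gap between MMRM and MI-ANCOVA has two possible causes instead of one.

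**Working it through.** **Plan's own figure.** The documents give no numerical target for the MMRM. The only stated figure is 94% power for the binary primary endpoint. With 37% vs 12%, 80 per arm, a continuity correction of 1/80 = 0.0125 and a mean rate of 0.245:

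- null SE = √(2 × 0.245 × 0.755/80) = 0.0680
- alternative SE = √((0.37 × 0.63 + 0.12 × 0.88)/80) = 0.0651
- z = (0.25 − 0.0125 − 1.96 × 0.0680)/0.0651 = 1.60, giving power of about 94.5%

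The stated power is reproduced. It has no bearing on this point.

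**Inputs from the documents.** 80 patients per arm; post-baseline visits at Weeks 2, 4, 8, 12 and 16; unstructured covariance; the fixed effects as listed.

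**Assumed inputs.** Slopes, residual variances, correlations and missingness. Absolute change is expressed in baseline-SD units with a true effect of 0.8. The planned model was compared with the same model plus baseline-by-visit, by maximum likelihood, with 300 to 500 trials per scenario. The added term was baseline-by-visit only; the stratum-by-visit part is not sized.

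| Outcome | Slope, Week 2 to Week 16 | Week 16 SE, planned ÷ with baseline-by-visit |
|---|---|---|
| Absolute change | -0.40 to -0.50 | 1.00–1.01 |
| Absolute change | -0.20 to -0.60 | 1.06–1.07 |
| Absolute change | -0.10 to -0.75 | 1.18–1.19 |
| Percent change, EASI-like | small | 1.00–1.02 |

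**Hand check with complete data.** The SE is approximately √(2 × residual variance/80).

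- Moderate case: residual variances 0.911 and 0.812 give √(2 × 0.911/80) = 0.151 and √(2 × 0.812/80) = 0.142, a ratio of 1.06. The simulated SEs were 0.1509 and 0.1428.
- Strong case: 1.295 and 0.907 give 0.180 and 0.151, a ratio of 1.19. The simulated SEs were 0.1798 and 0.1509.

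**A second simulation on the EASI scale.** Assumptions: baseline SD 12, slopes -0.25 to -0.70, residual SD 9.5, about 12% missing at Week 16, 150 trials. Empirical SDs were 1.556 and 1.473 (ratio 1.06). Mean model SEs were 1.586 and 1.536 (ratio 1.03). Each empirical SD carries about 6% Monte Carlo error.

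**Does the covariate form alone move the estimate?** In the moderate case with nothing missing, the Week 16 estimates from the two models differed from trial to trial with SD 0.05. That is 0.05/0.143 = 0.35 of a standard error. With 24 to 36% missing the SD was about 0.06.

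**Bias.** Under missing-at-random censoring, the mean shift between the two models was 0.013 to 0.022 (moderate) and 0.027 to 0.037 (strong). The largest is 0.037/0.8 = 4.6% of the effect. Under the null, in one percent-change scenario, rejection rates were 6.0% and 5.8%.

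**Cost of the term if it is not needed.** Where the percent-change slopes were equal at all visits, the SE ratio was 0.998 to 1.000.

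**The case against.** The strongest reply is that this is a modelling preference in a supportive analysis. Several parts of it stand.

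- **Most ranked endpoints are little affected.** The floor argument concerns absolute change. Of the four ranked continuous EASI and NRS endpoints, three are percent changes, where full clearance is -100% at any baseline. Only the Week 16 change in pruritus NRS is absolute. Absolute EASI change is a secondary endpoint but is not ranked.
- **The loss is conditional.** A reader might infer that the common slope is too steep at Week 2 and too shallow at Week 16, and that precision is therefore lost. The documents report no slopes, SDs or missing rates, so this cannot be asserted. With similar slopes the loss is 0 to 1%.
- **The plan has other checks.** A reader might infer that missing-data handling is never isolated. Sensitivity analyses 3 and 4 keep the ANCOVA covariates and change only the imputation.
- **Baseline-by-visit alone is not enough.** Stratum is also a main effect only, so the two models would still differ.
- **The missing-data assumption is shared.** MMRM and the main MI censor the same data and both rest on missing at random. Extra interactions do not change which assumption is tested.

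What remains is that the MMRM has its own stated purpose and its own reported estimates and p-values, and its covariate form differs from the ANCOVA for no stated reason.

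**Conclusion.** The point holds as a minor refinement. The text is clear that baseline and stratum enter the MMRM as main effects only. A difference between MMRM and MI-ANCOVA therefore cannot be attributed to missing-data handling alone, and the simulated estimates differed even with complete data.

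The precision loss depends on how far the slopes diverge and rests wholly on assumed inputs. The NRS was not simulated on its own scale.

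Nothing here supports a claim of material bias or an inflated error rate: the shifts were small and the null rejection rate was essentially the same under both models. MI-ANCOVA remains the main analysis of the continuous endpoints, so no primary or hierarchical result changes.

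**What to change.** In SAP sensitivity analysis 1, add baseline-by-visit and randomization-stratum-by-visit interactions for the EASI and pruritus NRS endpoints. With an unstructured covariance and complete data, the Week 16 comparison then coincides with the Week 16 ANCOVA, so any remaining gap reflects how the incomplete data are handled.

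The cost for EASI is 2 × (5 − 1) = 8 fixed-effect parameters. For NRS it depends on which time points enter the model, and the SAP should name them. If all 16 weekly averages are used, the cost is 2 × (16 − 1) = 30. No new data are needed, and SAP Section 1 allows revision on blinded review before database lock.
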